5.8 Rescue Medications for Acute Allergic Reactions

Treatment of individual acute allergic reactions during peanut OIT therapy should be with either an antihistamine and/or epinephrine, along with IV fluids, beta-adrenergic agonist (eg, albuterol), oxygen, and/or steroids, as indicated. Subjects and parents/guardians are likely already to have an epinephrine auto-injection device, but for those who do not, an epinephrine auto-injection device will be provided. The expiry dates for the epinephrine auto-injectors will be tracked and subject/families resupplied as necessary. Study staff must document in each subject's medical record that the subject and parent/guardian have been provided with an epinephrine autoinjection device and have been trained in its proper usage including injection technique.

5.9 Symptomatic Treatment for Chronic and/or Recurrent Adverse Events

Symptomatic treatment for chronic/recurrent AEs is permitted (except for prohibited medications [Section 5.10]), but should be used to supplement dose reduction, not substitute for it. It is advised that an attempt to withdraw symptomatic therapy be made prior to dose re-escalation. If

unsuccessful, symptomatic therapy may be resumed and dose escalation proceed with the symptomatic therapy in place. However, any therapy instituted for treatment of symptoms (AEs) related to study product, must be withdrawn by 4 weeks prior to Exit DBPCFC. If a subject is unable to tolerate a daily maintenance of 300 mg of study product for at least the last 4 weeks of dosing prior to Exit DBPCFC, free of any symptomatic therapy that was initiated during the course of OIT, the subject will be considered a nonresponder.

5.10 **Prohibited Medications**

- 1. Omalizumab (Xolair)
- 2. Systemic (oral) corticosteroids used for any greater duration than a total of 3 consecutive weeks throughout the study. If used, subjects must not be up-dosed during the 3 days after ceasing the administration of oral steroids
- 3. Beta-blockers (oral)
- 4. Angiotensin-converting enzyme (ACE) inhibitors
- 5. Angiotensin-receptor blockers (ARB)
- 6. Calcium channel blockers
- 7. Tricyclic antidepressants

During the course of the study, subjects may be at increased risk for anaphylaxis, which, in severe form, can result in a drop in blood pressure. Additionally, the administration of epinephrine to treat anaphylaxis can result in a sudden rise in blood pressure. For these reasons, the risks accompanying the use of any medication with known cardiovascular side effects must be weighed against the potential benefits of peanut OIT. This assessment must be performed for any medications being taken at study entry or added during the course of the study. The use of medication with known cardiovascular side effects during the course of the study is discouraged; but if an investigator deems use necessary, it must be undertaken with caution. It is beyond the scope of this protocol to list all drugs with cardiovascular side effects. Classes of drugs with a high potential for cardiovascular side effects include antipsychotics, cyclooxygenase 2 inhibitors (chronic use), non-steroidal anti-inflammatory drugs (chronic use), antiarrhythmics, antihypertensives, and antineoplastics. Before a drug with cardiovascular side effects is used in conjunction with OIT, the investigator should discuss its use with 1 of the study's Medical Monitors.

Immunomodulatory (including immunosuppressive) medications constitute another class of drugs whose use during the course of the study is generally prohibited. It is beyond the scope of this protocol to list all immunomodulatory drugs; broadly, these include drugs to treat or prevent transplant rejection, autoimmune disease, and certain neoplasias - examples include cyclosporine, tacrolimus, anti-tumor necrosis alpha drugs, and anti-IgE drugs. If an investigator contemplates the use of a potentially immunomodulatory drug during the course of the study, the investigator should discuss this with 1 of the study's Medical Monitors.

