6.6.2 Exit Double-Blind, Placebo Controlled Food Challenge (DBPCFC)

The Exit DBPCFC will be conducted in a manner similar to the Screening DBPCFC, but starting at a dose of 3 mg of peanut protein (except for subjects who failed their Screening DBPCFC at 1 mg), and with the last 3 challenge doses progressing from 300 mg (443 mg cumulative) to 600 mg (1043 mg cumulative) and then to 1000 mg (2043 mg cumulative) of peanut protein as shown in **Table 6-1**.

The same vehicle food should be used for the Exit DBPCFC as was used for the Screening DBPCFC.

Dosing with study product should continue on the days between the two parts of the Exit DBPCFC, according to the same dosing guidelines that apply throughout the Maintenance Period.

Subjects who failed their Screening DBPCFC at the 1 mg challenge dose of peanut protein will be required to start the Exit DBPCFC with a 1 mg dose. At the investigator's discretion, a 1 mg dose may be added at the beginning of the escalation (for a maximum cumulative dose of 2044 mg peanut protein) of any subject's Exit DBPCFC.

Subjects will be considered desensitization responders for the primary endpoint analysis for North America or Europe if they are able to tolerate an Exit DBPCFC challenge dose of 600 mg (1043 mg cumulative) or 1000 mg (2043 cumulative) of peanut protein with no, or only mild, symptoms, respectively.

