### 7.4. CLASSIFICATION OF RESPONDER STATUS

#### 7.4.1. Classification as a responder

To be a 600 mg responder, a subject must meet both of the following conditions:

- 1) Must have attained a maximum tolerated single dose (MTD) ≥600 mg of peanut protein on Exit DBPCFC
- 2) Must not have experienced more than mild symptoms through 600 mg of peanut protein on Exit DBPCFC.

Classification as a 300 mg responder and a 1000 mg responder are defined similarly.

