#### 7.4.2. Classification as a non-responder

If a subject cannot be classified as a responder, then that subject should be classified as a non-responder. If a subject meets any of the following conditions, then the subject is a non-responder:

- 1) Discontinued before the Exit DBPCFC or did not undergo an Exit DBPCFC for any other reason
- 2) Failed the Exit DBPCFC (e.g., a subject who did not tolerate a single dose of at least 600 mg of peanut protein with at most mild symptoms is a 600 mg non-responder).

Classification as a 300 mg non-responder and a 1000 mg non-responder are defined similarly.

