#### 7.4.4. Classification of Escalation and OIT Maintenance Failures

Non-responders who did not undergo the Exit DBPCFC are broadly categorized as either escalation failures or OIT maintenance failures. An escalation failure is a subject who is unable to achieve at least one at-home dose of 300 mg/d of peanut protein by 40 weeks (Protocol Section 3.2), discontinuing dosing prematurely either during the Initial Escalation period or during the Up-dosing period.

Subjects unable to tolerate a daily maintenance of 300 mg of study product for at least the last 2 weeks of dosing prior to Exit DBPCFC, free of any symptomatic therapy that was initiated during the course of OIT, will be considered OIT maintenance failures.

The 3 non-responder subcategories are summarized in Table 7.1.

Table 7.1 Non-Responder Subcategories for Subjects Who Do Not Undergo the Exit DBPCFC

Non-Responder Subcategory	Study Period Last Dose Was Taken	Definition of Period
Escalation Failure	Initial escalation	The last dose of study drug was taken during Initial Escalation Visit Day 1 or Day 2. No at-home doses were taken.
Escalation Failure	Up-dosing	The last dose of study drug was taken after Initial Escalation Visit Day 1 or Day 2 and before the first at-home dose of 300 mg.
OIT Maintenance Failure	Maintenance	At least one at-home dose of 300 mg was taken.

Classification of the primary reason a subject discontinued before the Exit DBPCFC provides a further sub-classification of non-responder subcategories, and will be determined during blinded data review prior to database lock and overall study unblinding.

The primary reason for discontinuation will be classified into one of the following categories:

- Discontinued due to reason related to treatment, including: escalation failure, OIT maintenance failure, treatment-related AE causing permanent discontinuation of study drug, or death
- Discontinued due to reason unrelated to treatment

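### A 4-week therapy-free condition for response (Protocol 5.9) becomes 2 weeks in SAP 7.4.4 and is missing from the SAP responder rule, so a child challenged too early can be classified two ways

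*Protocol*

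**What the plan says.** Protocol 5.9 deals with treatment of chronic or recurrent adverse events. Therapy started for product-related symptoms "must be withdrawn by 4 weeks prior to Exit DBPCFC". The next sentence makes a subject a nonresponder if unable to tolerate 300 mg/d for "at least the last 4 weeks of dosing prior to Exit DBPCFC, free of any symptomatic therapy" started during OIT. It is not limited to subjects who miss the challenge.

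SAP 7.4.4 has nearly the same sentence with a different number: "at least the last 2 weeks of dosing prior to Exit DBPCFC, free of any symptomatic therapy". Its consequence is the label of OIT maintenance failure. The scope is set at the start of that section: "Non-responders who did not undergo the Exit DBPCFC are broadly categorized as either escalation failures or OIT maintenance failures". Table 7.1 then assigns the maintenance label on one fact: "At least one at-home dose of 300 mg was taken".

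Responder status is defined elsewhere. SAP 7.4.1 begins "To be a 600 mg responder, a subject must meet both of the following conditions"; both conditions concern the challenge itself. SAP 7.4.2 makes a subject a non-responder who "Discontinued before the Exit DBPCFC or did not undergo an Exit DBPCFC for any other reason", or who failed the challenge. Protocol 6.6.2 also defines status by the dose tolerated: "Subjects will be considered desensitization responders for the primary endpoint analysis for North America or Europe" if they tolerate 600 mg or 1000 mg respectively with at most mild symptoms.

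Two other protocol rules are close to these. Section 6.3.5 requires the last 2 consecutive weeks at 300 mg/d to qualify for the challenge, with no condition on therapy. Section 9.2.1 fails subjects who do not achieve and maintain 300 mg/d, again with no condition on therapy.

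**The concern.** Responder status is the primary endpoint in both regions. The blinded pre-lock review in SAP 11 assigns it from SAP 7.4, where the therapy-free condition does not apply to anyone who was challenged. A condition that the protocol attaches to being a responder has thus changed length in one place and dropped out in another. SAP 12, whose heading concerns changes from the protocol's analysis, mentions neither.

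Two careful people classifying the same child, one from Protocol 5.9 and one from SAP 7.4.1, could reach opposite answers. If the question first arises after unblinding, whichever answer is chosen will look driven by the result.

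**Working it through.** **Step 1: subjects not challenged.** SAP 7.4.2 already makes every one of them a non-responder, and Table 7.1 sorts them by the period of their last dose. Whether 7.4.4 says 2 or 4 weeks changes no one's response status.

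**Step 2: subjects challenged.** Take a child at 300 mg/d who stopped an H2 blocker, begun for product-related GI symptoms, 3 weeks before the challenge and then tolerated 600 mg with mild symptoms.

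- Protocol 5.9, first sentence: breached, since 3 < 4 weeks.
- Protocol 5.9, second sentence: nonresponder, if being unable to tolerate the dose therapy-free for 4 weeks includes not having done so.
- Protocol 6.6.2 and SAP 7.4.1: 600 mg responder.
- Protocol 9.2.1: the dose was maintained, so no failure on that ground.

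The site could have avoided this. Protocol 6.11 lets the challenge fall within 2 weeks of the scheduled visit, enough to complete the fourth week. The case arises only when a child is challenged in breach of 5.9.

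**Step 3: Per Protocol analysis.** Protocol 9.2.3 plans it unconditionally. SAP 4.4 assures it only if the PP and Completer populations differ by more than 5% in an arm. Either way it removes a child whose breach is rated major; it does not settle that child's ITT status.

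**Step 4: scale.** The documents give no breach rate, so the size of the effect cannot be computed. What can be computed is how many reclassifications a significant result would absorb.

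Inputs: 495 children at 3:1, taken as 371 and 124 (Protocol 9.4); two-sided 5%; Farrington-Manning test with margin 0.15 (North America) or 0 (Europe) (Protocol 9.2.1). Planning rates are 50% vs 20% and 30% vs 15%; Phase 2 AR101 rates are 62% and 44% (Protocol 9.4).

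Formula: z = (p1 − p2 − d)/√[q1(1 − q1)/371 + q2(1 − q2)/124], where p1 and p2 are the observed rates, d is the margin, and q1, q2 are the maximum-likelihood rates under q1 − q2 = d.

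Check on the plan's own figures, with the restricted variance under the null and the unrestricted variance under the alternative: North America power is Φ[(0.15 − 1.960 × 0.04887)/0.04432] = Φ(1.22) = 88.9%, against about 89% stated. Europe is Φ[(0.15 − 1.960 × 0.04564)/0.03993] = Φ(1.52) = 93.5%, against at least 93% stated. Both reproduce.

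Starting point, North America: 186/371 = 0.5013, 25/124 = 0.2016, q1 = 0.4595, q2 = 0.3095, standard error 0.0489, so z = 0.1497/0.0489 = 3.06. AR101 responders are then moved to non-responder one at a time with placebo fixed, until z falls below 1.960:

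| Scenario | Responders, AR101 vs placebo | Starting z | Last significant | First non-significant | Share of AR101 responders |
|---|---|---|---|---|---|
| North America, 50% vs 20% | 186 vs 25 | 3.06 | 21 moved, z = 1.970 | 22 moved, z = 1.916 | 22/186 = 11.8% |
| North America, 62% vs 20% | 230 vs 25 | 5.26 | 65 moved, z = 1.970 | 66 moved, z = 1.916 | 66/230 = 28.7% |
| Europe, 30% vs 15% | 111 vs 19 | 3.20 | 23 moved, z = 1.967 | 24 moved, z = 1.910 | 24/111 = 21.6% |
| Europe, 44% vs 15% | 163 vs 19 | 5.72 | 75 moved, z = 1.967 | 76 moved, z = 1.910 | 76/163 = 46.6% |

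The 62% row pairs a Phase 2 active rate with a planning placebo rate. With no placebo responders at 600 mg, as in ARC001, 161 of 230 (70%) would have to move. Each move is worth 1/371 = 0.27 points.

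**The case against.** The strongest reply is that the plan can be read coherently. On that reading, Protocol 5.9 and 6.3.5 govern who reaches the challenge, and once it is done 6.6.2 gives the rule expressly for the primary analysis, which SAP 7.4.1 follows. A child challenged early is then a protocol deviation, recorded and rated blind under SAP 5, with the observed result kept in ITT as is usual. It can be added that the example child, who stayed at 300 mg/d and passed, has not clearly shown inability to tolerate the dose.

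This reading is available, and it is one of the two remedies below. But the documents do not adopt it. Section 5.9 names nonresponder status as the consequence and does not confine it to unchallenged subjects, and its withdrawal sentence points to the 4 weeks being required. Two defensible readings of a primary-endpoint rule are a reason to write one down.

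The 2 weeks in SAP 7.4.4 may come from Protocol 6.3.5. That would explain the number but not the text, since 6.3.5 concerns dose only and 7.4.4 adds the therapy condition.

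A reader might go further in three ways that the documents do not support:

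- That the plan is silent on such a child. It is not; Protocol 5.9 and SAP 7.4.1 each give an answer, and the answers differ.
- That the SAP's 2 weeks relaxes the responder standard. It cannot, because 7.4.4 covers only subjects already classed as non-responders.
- That following the SAP favours AR101. Hypersensitivity events were commoner on AR101 in ARC001 (90% vs 50%, Protocol 1.2.2.1), but those include acute reactions and do not count chronic therapy near the challenge.

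**Conclusion.** The inconsistency is real and touches the primary endpoint. The 4-week and 2-week texts differ without explanation, and the therapy-free condition is absent from the rule that will classify challenged children. That the example child is a nonresponder under the protocol rests on reading inability to tolerate as including a breach of the withdrawal sentence; this is the natural reading but not the only one.

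The number of affected children is unknown and probably small. The counts of 22 to 76 assume that every reclassified child is in AR101 and show scale, not materiality. No power loss or direction of bias is established, and a changed trial conclusion from this alone is unlikely. The point should be settled before lock because a blinded choice is cheap and an unblinded one can be challenged.

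**What to change.** While blinded and before database lock:

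1. In SAP 7.4.4, restore 4 weeks for the therapy-free condition, and keep the 2 weeks of Protocol 6.3.5 as the dose-only rule to qualify for the challenge. This is a consistency edit and changes no result by itself.
2. Choose one rule for challenged children. Either add to SAP 7.4.2 a non-responder condition for therapy started during OIT for chronic or recurrent product-related symptoms and still in use within 4 weeks of the Exit DBPCFC, expressly excluding single rescue doses for acute reactions, which Protocol 5.8 permits. Or declare in SAP 12 that 5.9 is only a condition for undergoing the challenge and that Protocol 6.6.2 governs once it is done.
3. Flag these children in the blinded review, report their number by arm after unblinding, and repeat the primary ITT analysis under the classification not chosen.

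The cost is a few lines of SAP text, one extra table, and an amendment under SAP 6.5 if the responder rule changes. The blinded check of medication stop dates against challenge dates may need site queries: as-needed medicines can stay on record without being taken (SAP 10.2), and partial dates are imputed (SAP 7.6).

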6 STUDY PROCEDURES

6.1 Enrollment and Randomization

Subjects will have an initial Screening DBPCFC consisting of both a peanut challenge and a placebo challenge before randomization. The peanut and placebo challenges will be conducted in a double-blind fashion, using foodstuffs provided by an unblinded site pharmacist, nutritionist, or study coordinator. Those subjects reacting to ≤ 100 mg of peanut protein (≤ 144 mg cumulative) will be randomized in a 3:1 ratio to AR101 or placebo. Those able to successfully consume the 100 mg top challenge dose of peanut protein during their DBPCFC, ie, do not develop dose-limiting symptoms, will not be eligible for the study. In addition, those reacting with dose-limiting symptoms to ≤ 100 mg of the placebo challenge will not be eligible for the study. Because of the requirement for the peanut DBPCFC, the screening and baseline visits will need to be conducted over more than 1 day.

Randomization will be stratified to maintain balance between treatment groups and to ensure adequate representation of key demographic sub-populations. Stratification will be by broad geographic region (to include at a minimum North America and Europe) and age (children from ages 4 to 17, inclusive, and adults to age 55, inclusive). As the Phase 2 studies (ARC001 and ARC002) were enrolled exclusively in the United States and only 1 adult subject was enrolled, stratifying randomization for age and geographic region will ensure balanced representation of potentially relevant subpopulations in ARC003. It is anticipated that approximately 65% of subjects will be recruited from North America, 30% from Europe, and potentially up to 5% from other regions. Investigational centers from Southern as well as Northern Europe are expected to participate. At least 80% of the subjects randomized will be children. Analysis of the ARC001 data showed no interactive effect of age on treatment effect (ie, desensitization), so stratification by age will include only the 2 strata, children and adults. As there is male predominance on the order of 2 to 1 in the peanut-allergic population below the age of puberty, randomization may be regulated to ensure adequate representation of girls younger than 12 years. But since the proportion of males and females randomized to each arm of the ARC001, a relatively small study, adequately reflected the literature-reported breakdown of the peanut-allergic population by gender, and there was no apparent effect of gender on desensitization, it is assumed that in ARC003, a relatively large study, the two arms will be adequately balanced for gender without stratifying for this independent variable. Further, although the prevalence of peanut allergy tends toward parity between males and females after the age of puberty, social factors can play a significant role in clinical trial participation, such that a given clinical trial population may not match exactly the disease population. Taking this into account, a target for the proportion of males to females recruited from the adolescent and adult peanut-allergic populations is not being set.

Randomization will be performed using an interactive response system.

The study procedures are tabulated in Appendix 1 and are listed per visit below.

6.2 Screening and Baseline

Screening may occur over several days and will include the following assessments/procedures:

• Informed consent and assent, as age appropriate

- Inclusion/exclusion criteria review
- Medical and allergy history review
- Concomitant medication review
- Diet (food allergen exposure) history review
- Completion of the food allergy related quality of life questionnaire (FAQLQ), and the food allergy independent measure (FAIM) questionnaire. Both questionnaires will be completed before the DBPCFC
- Assessment of asthma control using the Asthma Control Test questionnaire in subjects with asthma
- Physical examination, including weight and height
- Vital sign measurement (blood pressure, pulse rate, body temperature)
- Spirometry (FEV1) and/or Peak Expiratory Flow Rate (PEFR) prior to any DBPCFC; 3 attempts of FEV1 are performed and the best value is taken; 3 attempts of PEFR are to be performed, and the best value taken. PEFR should be measured at the same time for each visit assessment.
- Serum pregnancy test, for females of childbearing potential
- Blood draw to collect samples for:
 - Peanut-specific IgE, component-resolved IgE (including at screening determination of Ara h 1, Ara h 2, Ara h 3, Ara h 8 and Ara h 9) peanut IgE, total IgE, and peanut-specific IgG4 (immunoglobulin assays) The amount of blood to be taken for the immunoglobulin assays will be communicated from the central laboratory and included in the manual of procedures.
 - Complete blood cell count (CBC), obtained with the same venipuncture as the blood draw for the immunoglobulin assays
 - Optional exploratory immune cell characterization by the Immune Tolerance Network (ITN). Note that these samples can be obtained with the same venipuncture as the blood draw for the immunoglobulin assays and CBC, but will require an addition volume of blood to be collected. Separate informed consent is required.

The amount of blood to be taken in total for the above assays (required immunoglobulin assays, required CBC, and optional immune cell characterization assays) will not exceed a total volume of 0.67 mL/kg in children, to a maximum of 50 mL, total, in 8 weeks. Blood draw should be collected in compliance with local laboratory guidelines and testing regulations.

- Skin prick test to peanut extract
- DBPCFC conducted in accordance with PRACTALL guidelines, with assessments made by a Blinded Evaluating Physician (Blinded Assessor), as described in Section 6.6
- (North America sites only) Optional collection of saliva sample for exploratory biomarker development (Appendix 6)
- Monitoring for adverse events (AEs), including allergic symptoms (Section 6.7)

- Subjects will be instructed to continue to follow a peanut-avoidant diet for the duration of the study.
- Subjects and parents or guardians will additionally receive teaching about food/peanut allergy according to the investigational site's established standards. This is to include at a minimum the following topics (some or all of which may be addressed in a comprehensive anaphylaxis action plan):
 - Recognition of an allergic reaction and of the symptoms of anaphylaxis
 - When and how to administer epinephrine via auto-injector
 - Requirement to go to nearest emergency facility following use of epinephrine autoinjector
 - Ways to minimize the risk of accidental exposure to peanut in, and outside of, the home (may be supplemented by referral to recognized food allergy organizations for access to additional learning materials)

All screening procedures must be completed no later than 28 days from the signing of the informed consent/assent form. The Initial Escalation Day-1 visit should occur within 10 days of the Screening DBPCFC.

The laboratory values and clinical findings, including those from the Screening DBPCFC, will serve as the baseline measures for comparison to subsequent measures obtained during the course of the study.

